5.2 Efficacy Analysis by Line of Therapy

Efficacy analyses will include analysis by current line of therapy (3rd line and ≥3rd line) in the modified ITT population. Efficacy analyses by current line of therapy (3rd line and ≥3rd line) in the efficacy evaluable population will be included for all endpoints except for overall survival.

5.3 Subgroup Analyses for Primary Endpoints

The following subgroup analyses will be performed for the primary endpoints of ORR and OS for DLL3 high and DLL3 positive subjects in the modified ITT population.

- Current line of therapy (3rd, 4th, >4th)
 - Determined based on regimen. It will be the last regimen number +1
- Response to frontline therapy (sensitive, refractory, resistant, and resistant/refractory)
- Prior systemic therapies (drug categories) that may include the following:
 - Topotecan
 - Immunotherapy (Yes, No; includes PD-1 inhibitor and other immunotherapy)
- Prior cancer surgery (Yes, No)
- Prior radiation therapy (Yes, No)
- History of brain metastases (Yes, No)
- Presence of brain metastases at baseline (Yes, No)
- ECOG at baseline (0, 1, >1)
- Baseline tumor burden (<Q1, Q1- Q3 inclusive, > Q3; where Q1 and Q3 are the quartile values of the baseline sum of the longest diameters of target lesions per IRC assessment)
- Gender (Male, Female)
- Grouped race (White, Non-White)
- Age group (<65, ≥65 years)

- U.S. vs non-U.S. sites

In addition to above subgroups, subgroup analysis of OS will also be performed by

- Objective response (determined by IRC and investigator assessments) to rovalpituzumab tesirine therapy (CR/PR, Non-CR/PR)
- Best overall response (determined by IRC and investigator assessments) to rovalpituzumab tesirine therapy (CR/PR, Non-CR/PR and the subcategories of SD, PD, NE/Early Death/Indeterminate)
- Clinical benefit (determined by IRC and investigator assessments) to rovalpituzumab tesirine therapy (Yes, No)
- Time to progression on second line (2L) therapy, defined as time from start of 2L therapy to the last progression on 2L therapy (≤ 3 months, > 3 months).

6. ANALYTIC DEFINITIONS

Initial Treatment Period includes all assessments prior to the retreatment period or the start of new anti-cancer therapy, whichever occurs earlier. For subjects who will not be retreated, the initial treatment period will include assessments till the start of new anti-cancer therapy or the end of study, whichever occurs earlier.

Baseline Evaluation is the last available evaluation prior to receiving first dose of study drug. This will include any unscheduled evaluation prior to first dose. For subjects receiving retreatment, baseline for that period is the last available evaluation prior to receiving first dose of study drug for retreatment.

Change from Baseline is defined as the difference between the baseline value as defined above and the value at the respective time point. Negative values represent decreases from baseline; positive values will reflect increases from baseline.

Percent Change from Baseline is defined as the change from baseline divided by the baseline value times 100%. That is

$$100x (\text{Post-baseline value} - \text{baseline value}) / (\text{baseline value}).$$

Age at Baseline (in years) is defined from date of birth to date of first dose.

Last Evaluable Disease Assessment, for purpose of censoring, will be the last assessment with a response that is determined to be CR, PR, SD, PD, or Not Evaluable (NE).

Treatment-Emergent Adverse Event during this period is defined as any adverse event occurring on or after initiation of therapy and prior to the earlier of the start of retreatment period for those received Rova-T retreatment and the start of a subsequent anti-cancer therapy. Any adverse event with onset on or after the first dose of retreatment till the start of the next retreatment period or the start of a subsequent anti-cancer therapy will be considered treatment-emergent for that retreatment period.

Concomitant Medication is defined as a medication or treatment other than the study drug is considered concomitant if it is taken at any time on or after the first dose date. A medication taken prior to first dose date and continuing past first dose date is considered concomitant. Concomitant medications that stopped prior to first dose of retreatment will only be included in the initial treatment period. Medications started after the first of retreatment will be considered concomitant during the retreatment period.

Cumulative Actual Dose (in mg) is the sum of actual dose. Cumulative dose will be summarized for both initial treatment period and retreatment period.

Treatment Duration (in cycles) is defined as number of cycles begun where rovalpituzumab tesirine dose is greater than zero.

Response to Frontline Therapy (sensitive, refractory, resistant)

- Refractory: For 1st Regimen if response is 'PD' (if first Regimen is 'NE' then 'NE')
- Sensitive: If not Refractory and not 'NE' and if (First of Regimen 2 start date – Last of Regimen 1 End Date, excluding placebo) +1 \geq 90 days
- Resistant: If not Refractory and not 'NE' and if (First of Regimen 2

start date – Last of Regimen 1 End Date) +1 < 90 days

- Note: Impute partial date of start or stop date as follows: If month and day both missing for one of the two dates in comparison and the year is different, the duration considered >= 90 days. If the year is the same then response is considered ‘Undetermined’
- If only Day is missing then based on the month and year derive the months of duration to compare with 3 months duration and determine sensitive or resistant

Note: If the response for the first regimen is ‘NE’ then the response to frontline therapy for that subject is classified as a ‘Not Evaluable’

Pack Years of Smoking is defined as:

(Number of cigarettes smoked per day/20) * Number of years smoked

QTcF is defined as:

$$QTcF = QT / (\sqrt[3]{RR})$$

Tumor Burden is based on the sum of the target lesions at baseline, where baseline is defined as the last lesion measurement on or prior to first dose.

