9.2.1.3 Handling of Dropouts and Missing Data

With the exception of time-related endpoints, no imputation will be conducted for missing data unless otherwise specified in the SAP. For time-related endpoints (e.g., duration of response), subjects who have no specified event will be censored at the time of the last valid assessment of the endpoint(s).

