7.5.1 Objective Response Rate

Overall Response at each visit post-baseline is assessed based on a subject's lesion measurements or assessments. Overall Response is assessed as CR, PR, SD, PD, or NE as defined by RECIST version 1.1. An additional category of Early Death will also be included which is defined as subjects who died prior to any post-baseline response assessment. Amongst all the Overall Responses, the best Overall Response is then determined. The best Overall Response will be ordered as CR, PR, SD, PD, or NE; with CR being the best. A subject will be considered to have a best overall response of SD if there is a minimum interval of 42 days between the date of assessment and (-7 days to allow for scheduled visit window per the protocol) the first dose date. Subjects who died prior to the first post-baseline lesion assessment are included in the Early Death category. The Not Evaluable (NE) category includes subjects who are not evaluable as indicated by the IRC or by the Investigator, in analyses of overall response per IRC and investigator, respectively. Subjects who discontinued the study prior to obtaining a post-baseline scan for lesion assessment will be categorized as Indeterminate.

Objective Response is defined as a subject with the best Overall Response of Complete Response (CR) or Partial Response (PR) prior to receiving any subsequent anticancer therapy and retreatment, and is confirmed by a consecutive response assessment at least 4 (28 days) from the initial determination of CR/PR per RECIST v 1.1 as described in Table 1:

Table 1 – Confirmed partial and complete response

Overall response First time point	Overall response Subsequent time point	BEST overall response
CR	CR	CR
CR	PR	SD, PD or PR ^a
CR	SD	SD (if minimum duration for SD met), otherwise, PD
CR	PD	SD (if minimum duration for SD met), otherwise, PD

CR	NE	SD (if minimum duration for SD met), otherwise, NE
PR	CR	PR
PR	PR	PR
PR	SD	SD
PR	PD	SD (if minimum duration for SD met), otherwise, PD
PR	NE	SD (if minimum duration for SD met), otherwise, NE
NE	NE	NE

Note: In case of SD, measurements must have met the SD criteria at least once after study entry at a minimum interval of 42 days (-7 days to allow for scheduled visit window per the protocol).

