7.6.1 Duration of Response

Duration of objective response is defined as the time in months from the initial CR or PR to the time of disease progression or death on study, whichever occurs first during the initial treatment period. Only subjects with a confirmed response of CR or PR will be included.

For subjects who are alive and have not experienced disease progression on the study, duration of objective response will be censored at the day of the last tumor assessment during the initial treatment period. If no tumor assessment after the initial response is available, then the duration of response will be one day. Censoring rules for duration of response will be performed as detailed in [Table 3](#). If multiple visits exist, the latest

evaluable assessment date will be used for censoring except for PD, which will use the earliest assessment date when PD was recorded. Symptomatic deterioration will not be considered PD since a lesion assessment will need to be performed to verify disease progression. If there are multiple scans with multiple dates provided for a visit, the lesion assessment date will be the last scan date recorded for that visit to define baseline and the earliest scan date within the visit to determine the lesion assessment date post-baseline.

Table 3 - Duration of Response Censoring Methodology

Situation	Date of Progression/Death or Censoring	Outcome*
Death or disease progression per RECIST 1.1 at any time during initial treatment period	Date of death or first disease assessment showing disease progression, whichever occurs first	Event
Progression caused by new lesion during initial treatment period	Date new lesion is detected	Event
Progression caused by worsening of non-target lesion(s) or target lesion(s) during initial treatment period	First assessment date documenting the increase in target lesion(s) meeting criteria for progression, or the worsening non-target lesion(s)	Event
Progression caused by multiple causes (e.g. new lesions and worsening of non-target lesions) during initial treatment period	First date among the multiple sources of PD	Event
Subsequent anti-cancer treatment started before death or without documentation of disease progression beforehand	Date of last evaluable disease assessment prior to start of subsequent anti-cancer treatment	Censored

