Death or disease progression after missing two or more consecutively scheduled disease assessments during initial treatment period	Date of last evaluable disease assessment visit without documentation of disease progression that is before the missed visit	Censored
Alive and without documentation of disease	Date of last evaluable	Censored

progression during initial treatment period	disease assessment during initial treatment period	
---------------------------------------------	----------------------------------------------------	--

*Time (month) = (Date of Progression/Death or Censoring – Date of first response (CR or PR) + 1)/ 30.44.

For Duration of Objective Response, only subjects with a confirmed response of CR or PR will be included.

Duration of objective response will be estimated using the Kaplan-Meier method. The median duration of objective response and the corresponding 2-sided 95% confidence interval will be produced in addition to the range. The proportion of responders who have not yet experienced disease progression or death at 6, 9, and 12 months from the start date of CR or PR will be summarized descriptively based on Kaplan-Meier estimates. The estimates will be accompanied by a two-sided 95% CI.

Duration of best overall response will also be summarized. This analysis will include subjects with a response of CR or PR, regardless of confirmation.

Duration of objective response and duration of best overall response will be summarized based on IRC assessments, as well as investigator assessments.

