7.6.3 Duration of Clinical Benefit

DOCB [CR, PR, or SD with SD of a minimum duration of 42 days (-7 days to allow for scheduled visit window per the protocol from the first dose date)] is defined as time in months from the initial CR, PR, or SD to the time of disease progression or death on

study, whichever occurs first during the initial treatment period. Only subjects with the response of CR, PR, or SD are included.

For subjects who are alive and have not experienced disease progression on the study, DOCB will be censored at the day of the last tumor assessment during the initial treatment period. Censoring rules for duration of clinical benefit will be performed as detailed in Table 3 above. If multiple visits exist, the latest evaluable assessment date will be used for censoring except for PD, which will use the earliest assessment date when PD was recorded. Symptomatic deterioration will not be considered PD since a lesion assessment will need to be performed to verify disease progression.

DOCB will be estimated using the Kaplan-Meier method. The median duration of clinical benefit and the corresponding 2-sided 95% confidence interval will be produced in addition to the range.

Calculation of DOCB will be based on IRC assessments, as well as investigator assessments.

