7.6.4 Progression-Free Survival

PFS is defined as the time in months from the first day of study drug administration (Day 1) to disease progression or death on study, whichever occurs first during the initial treatment period.

For subjects who are alive and have not experienced disease progression during the initial treatment period, PFS will be censored on the day of the last tumor assessment during the initial treatment. Subjects with no post-baseline response assessment PFS will be censored and have a PFS duration of one day. Censoring rules for PFS will be performed as detailed in Table 4 below. If multiple dates exist for a given visit, the latest evaluable assessment date will be used for censoring except for PD, which will use the earliest assessment date when PD was recorded. Symptomatic deterioration will not be considered PD since a lesion assessment will need to be performed to verify disease progression.

Table 4 – Progression-Free Survival Censoring Methodology

Situation	Date of Progression/Death or Censoring	Outcome*
Death or disease progression per RECIST 1.1 at any time during initial treatment period	Date of death or first disease assessment showing disease progression, whichever occurs first	Event
Death before first planned disease assessment	Date of death	Event
Progression caused by new lesion during initial treatment period	Date new lesion is detected	Event
Progression caused by worsening of non-target lesion(s) or target lesion(s) during initial treatment period	First assessment date documenting the increase in target lesion(s) meeting criteria for progression, or the worsening non-target lesion(s)	Event
Progression caused by multiple causes (e.g. new lesions and worsening of non-target lesions) during initial treatment period	First date among the multiple sources of PD	Event
Subsequent anti-cancer treatment started before death or without documented disease progression	Date of last evaluable disease assessment prior to start of non-protocol anticancer treatment	Censored
Death or disease progression after missing two or more consecutively scheduled disease assessments during initial treatment period	Date of last evaluable disease assessment visit without documentation of disease progression that is before the missed visit	Censored
Alive and without documentation of disease progression during initial treatment period	Date of last evaluable disease assessment during initial treatment period	Censored

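### SAP Section 6 counts Not Evaluable reads as evaluable for censoring, so PFS, DOR and duration of clinical benefit can be censored at a scan that did not establish freedom from progression; the effect is small and upward

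*SAP*

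**What the plan says.** SAP Section 6 (Analytic Definitions) states that, for censoring, the last evaluable disease assessment "will be the last assessment with a response that is determined to be CR, PR, SD, PD, or Not Evaluable (NE"). The list includes NE. It also includes PD, which is an event and not a censoring status.

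The definition feeds three endpoints:

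- **PFS.** All three censoring rows of SAP Table 4 (new anticancer therapy, event after two or more missed assessments, alive without progression) use the last evaluable assessment.
- **Duration of response (DOR).** The three censoring rows of SAP Table 3 do the same. Section 7.6.1 also plans a duration of best overall response: "This analysis will include subjects with a response of CR or PR, regardless of confirmation".
- **Duration of clinical benefit (DOCB).** Section 7.6.3 refers to Table 3.

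The running text uses a different term. In 7.6.1, "duration of objective response will be censored at the day of the last tumor assessment during the initial treatment period", with no evaluability condition; 7.6.3 and 7.6.4 are similar. Section 7.6.3 adds: "If multiple visits exist, the latest evaluable assessment date will be used for censoring except for PD".

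Two other places bear on the point. Protocol 9.2.1.3 says that subjects without an event "will be censored at the time of the last valid assessment of the endpoint(s"). In SAP Table 1 (Section 7.5.1), a PR followed by NE gives a best response of "SD (if minimum duration for SD met), otherwise, NE", so an NE read does not confirm a response.

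**The concern.** A censoring date should be the last time at which the subject was known to be event-free. An NE read does not establish that. Under Section 6 it still extends the time credited as progression-free, or as time in response.

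Nothing else in the SAP cures this. The reference in 7.6.3 to the latest evaluable date takes its meaning from Section 6, where NE counts as evaluable. The phrase last tumor assessment is wider still.

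What is at stake is a one-directional shift in the reported PFS and DOR curves, their medians and the 6-, 9- and 12-month estimates. The trial has a single arm, so no control group subject to the same rule offsets the shift. The SAP specifies no censoring sensitivity analysis for these endpoints that would show it.

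**Working it through.** The documents state no PFS, DOR or DOCB figure, so there is none to reproduce. The check has three parts.

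**1. Single subjects.** SAP formula: months = (censoring date − first dose date + 1)/30.44, which is study day/30.44. Scans are every 6 weeks to 6 months, then every 12 weeks (Protocol Appendix 12.1).

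| Reads | As written | NE excluded |
|---|---|---|
| SD day 42, NE day 84, then new therapy | 84/30.44 = 2.76 | 42/30.44 = 1.38 |
| SD day 168, NE day 252, no later scan | 252/30.44 = 8.28 | 168/30.44 = 5.52 |
| Only post-baseline read is NE, day 42 | 42/30.44 = 1.38 | 1/30.44 = 0.03 |

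In the second row the subject is carried past the 6-month landmark on a scan that did not show progression status.

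**2. Direction.** At each event time the Kaplan-Meier factor is 1 − d/r, with d events and r at risk. If events are unchanged, counting NE moves censoring dates later or leaves them alone. Then r is the same or larger, d is the same, and each factor is the same or higher. The curve as written can never lie below the one with NE excluded. In 5,000 simulated trials of 123 there were no exceptions, as the algebra requires.

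The condition matters. The SAP does not say whether an attended scan read as NE counts as missed in the two-missed-assessments rows. The sequence SD, NE, NE, PD is an event at PD if it does not, and is censored at the SD scan if it does.

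**3. Size.** All rates are assumptions. Protocol 1.1.1 (time to progression of 3-4 months with second-line topotecan, survival under 6 months in recurrent disease) serves only as an anchor. For PFS: median time to progression 3, 4 or 5 months; median OS 6 months; scans at days 42, 84, 126 and 168, then every 84 days; drop-out 3% or 6% per month; data cut at 6-24 months; 400,000 subjects per scenario.

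| Assumption | Rise in 6-month PFS, percentage points |
|---|---|
| 5-20% of scans NE at random | 0.12 to 1.01 |
| 30-50% of censored subjects have an NE last scan | 0.78 to 2.23 |
| 30-50% of censored subjects have NE at the last two scans | 1.75 to 4.55 |

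The ends of the first row are 13.97% against 13.85% (time to progression 3 months, 5% NE, 3% drop-out) and 23.75% against 22.74% (5 months, 20% NE, 6% drop-out). Under random NE the rise is 0.11-0.97 points at 9 months and 0.06-0.70 at 12; the median moves by 0-0.1 month. The share of subjects affected is 0.6-4.3%, about 1-5 of 123.

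Drop-out drives the size. At 15% monthly drop-out the 6-month rise reaches 1.9 points. In a separate model with 10-25% of subjects stopping scans after each visit, it is 0.1-2.5 points, with 0-0.27 month on the median.

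For confirmed DOR (median to progression 4 or 6 months, median OS 9 months, 5-20% NE) the rise is 0.24-1.65 points at 6 months, 0.33-2.01 at 9 and 0.27-1.83 at 12. The largest median shift is 6.27 against 5.91 months. For unconfirmed response the 6-month rise is 0.20-1.41 points. The DOCB median does not change (2.79 months).

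**The case against.** *The effect is negligible.* With 123 subjects and 6-month PFS near 19%, the 95% half-width, ignoring censoring, is 1.96 × √(0.19 × 0.81/123) = 6.9 points. A shift of 0.1-1.0 points is well inside that, and the larger figures need NE patterns that the documents neither support nor exclude. This stands as a limit on importance. It does not make the definition right: the shift is systematic and free to remove.

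*An NE scan may still carry information.* Protocol Appendix 12.4 makes any new lesion progression, so an incomplete scan can still show PD. That is fair, and it would be too strong to call such scans uninformative. They do not, however, establish that the subject was progression-free, which is what a censoring date asserts.

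*Confirming a response and dating censoring are different questions.* Correct. Table 1 shows how little weight NE carries elsewhere; it is not a contradiction.

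*The SAP breaches the protocol.* A reader might infer this from Protocol 9.2.1.3. The documents do not support it: that section leaves the word valid undefined, and Protocol 9.2.6.2.3 refers PFS censoring to a regulatory guidance that is not reproduced.

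*Early deaths are lost from PFS.* A reader might infer this from 7.6.4: "Subjects with no post-baseline response assessment PFS will be censored and have a PFS duration of one day". That sentence does not repeat the limit to living subjects in the sentence before it. But the next sentence defers to Table 4, which has an explicit row counting death before the first planned assessment as an event. If Table 4 is followed, the effect is zero. This is an editorial ambiguity.

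*Declaring NE not missed is itself a choice.* It is. It keeps the plain reading of those rows and leaves events unchanged, but it is a convention to be stated, not a correction. With NE excluded, also treating it as missed would turn 0.2-5.8% of subjects from event to censored and move 6-month PFS by −0.2 to +0.2 points.

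**Conclusion.** The definition is wrong as written, and the effect is small. NE is listed as evaluable, every censoring row of Tables 3 and 4 depends on that term, and no other text removes it. The upward direction is certain when events are unchanged, which requires that an attended NE scan is not treated as missed. The size rests wholly on assumed NE and drop-out rates: about 0.1-1.0 points on 6-month PFS and 0-0.1 month on the median under random NE at 5-20% and 3-6% monthly drop-out, and more with heavier drop-out or NE clustered at the last scans.

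PFS, DOR and DOCB are analysed descriptively here. ORR, OS, the interim rule and the sample size do not use this definition. The point belongs at the lower end of what should be changed.

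**What to change.** 1. **SAP Section 6.** Define the last evaluable disease assessment for censoring as the last assessment of CR, PR or SD, excluding NE. PD drops out of the list as well.
2. **SAP 7.6.1, 7.6.3 and 7.6.4.** Use that term in place of last tumor assessment. DOR and DOCB need no further rule. The scan that starts the duration is itself evaluable, so a subject with only NE reads afterwards has a duration of one day, in line with 7.6.1: "If no tumor assessment after the initial response is available, then the duration of response will be one day".
3. **Tables 3 and 4.** State that an attended scan read as NE is not a missed assessment for the two-missed-assessments rows.
4. **SAP 7.6.4, editorial only.** State that Table 4 governs. An unscanned death before the first planned assessment, with no new anticancer therapy before it, is an event on the date of death. The one-day rule applies only to subjects censored under Table 4 with no evaluable post-baseline assessment.

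The cost is a few sentences before database lock, with no new data. Reported PFS and DOR may be slightly less favourable. Subjects whose only post-baseline reads are NE (0.2-1.4% under the 5-20% assumption) move to Day 1 censoring for PFS.
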